Protocol ARC001 Synopsis Title Oral Desensitization to Peanut in Peanut-Allergic Children and Adults using Characterized Peanut Allergen (CPNA) Peanut Oral **Immunotherapy (OIT) CPNA Peanut OIT Short Title** 2 **Clinical Phase** 15463 IND Allergen Research Corporation (ARC) **IND Sponsor** Approximately 50 peanut allergic subjects will be randomized 1:1 to peanut Number of Subjects Oral Immunotherapy (OIT) versus placebo. The primary objective is to demonstrate the efficacy of Characterized Peanut Objective Allergen through reduction in clinical reactivity to limited amounts of peanut allergen in peanut-allergic children and young adults (ages 4-26 years, inclusive). The secondary objectives are: • To demonstrate the safety of Characterized Peanut Allergen as measured by incidence of adverse events and dosing symptoms. • To evaluate the immunological effects of peanut OIT therapy. • To determine the time course of tolerated up-dosing • To evaluate safety based on physician global assessment of disease activity This is a multicenter, randomized, double-blind placebo-controlled study of **Study Design** efficacy and safety of characterized peanut OIT in peanut allergic individuals. The study will consist of a screening period, a double-blind OIT treatment (up-dosing and maintenance) period, followed by a double-blind, placebo controlled food challenge (DBPCFC). An open-label safety followup study (ARC002) is planned after completion of ARC001. All eligible subjects will receive an escalating dose of either characterized peanut allergen or placebo. Beginning at Week 22, eligible subjects who reach the targeted daily dose of 300 mg/day and maintain that dose for 2 weeks will undergo a DBPCFC. Subjects who have not reached 300 mg/day will continue to up-dose as tolerated until they are eligible for the DBPCFC (after 2 weeks home dosing with 300 mg/day) or until they reach Week 34, at which time they will be considered an escalation failure. A DBPCFC will be performed for those subjects achieving the target dose of 300 mg and continuing to receive that dose for 2 weeks. Each subject will be unblinded when he/she completes the DBPCFC at the end of 2 weeks treatment with 300 mg/day. All placebo subjects are eligible for rollover into the ARC002 protocol. Placebo subjects in ARC002 will undergo an escalation schedule identical to that for active subjects in the ARC001 protocol. All subjects on active treatment who pass the DBPCFC are eligible to proceed to ARC002. Those who do not pass will be considered endpoint failures. A Data Monitoring Committee (DMC) has been established for the study to monitor the study for safety. 6 to 9 months **Study Duration**

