All subjects who reach and tolerate 300 mg/day for 2 weeks will undergo an exit DBPCFC. Those unable to achieve a dose of 300 mg/day of peanut protein by 34 weeks will be considered escalation failures and will not undergo an exit DBPCFC.

During the treatment period, the subjects will be monitored for tolerability as illustrated in Figure 6–1 and Figure 6–2 (see Section 6.8.4).

If a subject is removed from therapy because of failing escalation during the initial escalation period (Visit 1; Days 1 to 3), the subject will be followed for safety and asked to return to the Clinical Research Center 14 days following their last dose of study product to undergo an Early Discontinuation Visit (see Section 6.5).

If a subject's up-dosing is halted because of failing subsequent build-up (i.e., after the initial escalation period; Visit 1), the subject will continue to be dosed at the last tolerated dose level and to be followed for safety biweekly (following their established visit schedule) until Week 24, i.e., a maintenance phase (See also Section 6.8.4). Dosing will be stopped after the Week 24 Visit; and the subject will be asked to return to the Clinical Research Center 14 days following their last dose of study product to undergo an Early Discontinuation Visit (see Section 6.5).

For subjects who halt dose-escalation after Week 24, there will be no maintenance phase. Dosing in these subjects will be discontinued when dose-escalation is stopped. They will be followed for safety and asked to return to the Clinical Research Center 14 days following their last dose of study product to undergo an Early Discontinuation Visit (see Section 6.5).

For subjects who achieve the targeted dose of 300 mg/d by Week 34, the maintenance phase comprises the last two weeks of the study.

Subjects who prematurely discontinue treatment before Week 24 for any reason will be brought in for an early discontinuation visit 14 days after their last dose.

A Data Monitoring Committee (DMC) has been established and will meet every 3 months to monitor the study for safety.

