3.3 Exit DBPCFC

All subjects who reach the targeted daily dose of 300 mg/day and maintain that dose for 2 weeks will undergo an exit DBPCFC. The exit DBPCFC will be performed in accordance with PRACTALL guidelines, but requiring progression in an unaltered sequence (Table 6-2), without repeating any dose.

Each subject will be unblinded after he/she completes the DBPCFC.

Subjects who do not reach the target dose by Week 34 are not eligible for the exit DBPCFC, and will be considered escalation failures. They will be unblinded no sooner than Week 24.

All placebo subjects are eligible for rollover into ARC002. Placebo subjects enrolled in ARC002 will undergo an escalation schedule identical to that for active subjects in the ARC001 protocol. All subjects on active treatment who pass the DBPCFC are eligible to proceed to ARC002. Subjects in the active treatment group who do not pass the DBPCFC at the 300 mg (443 mg cumulative) protein level will be considered endpoint failures and will not be eligible for rollover into the ARC002 protocol.

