6.5 Visit 03 - Exit Visit / Early Discontinuation Visit

Subjects who tolerate 300 mg/day and are maintained at this dose for 2 weeks will return to the clinic for an Exit visit. For these subjects, the Exit visit will occur at approximately 6-9 months post-Visit 01.
Subjects who fail escalation or build-up, or who prematurely discontinue treatment, will return to the site for an Early Discontinuation visit that consists of the same procedures as the Exit visit, but without a DBPCFC or associated optional blood draws. An Early Discontinuation visit is to occur 14 days from the last dose of study product.

The following procedures will be performed at the Exit visit:

- Medical/allergy history
- Concomitant medications
- Physical exam, including weight and height
- Vital signs (blood pressure, pulse rate, body temperature)
- PEFR (3 attempts are to be performed, and the best value taken). PEFR should be measured at the same time for each visit assessment.
- Urine pregnancy test, for females of childbearing potential
- Diet history
- Blood draw for peanut-specific IgE and IgG4 measurement (mechanistic assays), the amount to be specified by local laboratory guidelines.
- Optional blood draw (pre-DBPCFC) for exploratory analysis by ITN. The amount taken should be 5 mL/kg in children weighing ≥30 kg, with a maximum of 60 mL in total. Blood draw should be collected per NIH guidelines.
- Skin prick test to peanut extract
- Physician global assessment of disease activity using a 100-mm VAS
- Monitoring for compliance and allergic symptoms

In addition to the procedures listed above, eligible subjects will have an exit DBPCFC performed. Eligible subjects are those who tolerate 300 mg/day and are maintained at this dose for 2 weeks.

For placebo subjects only:

• Exit DBPCFC conducted in accordance with PRACTALL guidelines as described in Section 6.6.2, then proceed to ARC002

For active-treatment subjects completing DBPCFC only:

• Proceed to ARC002

Each subject participating in the study will be unblinded when he/she completes the Exit visit procedures (including the exit DBPCFC for eligible subjects).

6.6 Double-Blind, Placebo Controlled Food Challenge (DBPCFC) in accordance with PRACTALL guidelines

The DBPCFC is performed by feeding gradually increasing amounts of the suspected food under physician observation.^{25,26} A sample of food challenge from the PRACTALL guidelines using peanut flour is given in Table 6-1.

Challenge Doses				

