6.13 Study Blinding Procedures

The study is double-blinded up to completion of the exit DBPCFC, escalation failure, or endpoint failure.

Those who are not eligible for the DBPCFC at Week 34 will be unblinded at this time.

Those who do not pass the DBPCFC at Week 36 will be unblinded at this time.

All food challenges are performed in a double-blind manner.

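### Protocol 6.13 unblinds late escalation failures at Week 34, up to about two weeks before their only post-baseline physician VAS, whereas Protocol 6.5 and SAP 7.8 unblind only after the final-visit procedures

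*Protocol*

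**What the plan says.** The protocol and SAP give several rules for when a subject is unblinded.

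- **Protocol 6.13** opens with a general rule: "The study is double-blinded up to completion of the exit DBPCFC, escalation failure, or endpoint failure". It then gives a dated instruction for subjects who have not qualified for the exit food challenge: "Those who are not eligible for the DBPCFC at Week 34 will be unblinded at this time".
- **Protocol 6.5** has a different order: "Each subject participating in the study will be unblinded when he/she completes the Exit visit procedures". SAP 7.8 agrees with 6.5. It unblinds after the final visit and study exit, and it covers subjects who miss the final assessments by unblinding them after they leave the study.
- **Protocol 3.3 and 4.3.1** set a floor: escalation failures are not unblinded before Week 24.
- **The synopsis** ("Each subject will be unblinded when he/she completes the DBPCFC at the end of 2 weeks treatment with 300 mg/day") and **Protocol 3.3** ("Each subject will be unblinded after he/she completes the DBPCFC") tie unblinding of challenged subjects to completing the challenge.

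The visit timing comes from Protocol 3.2 and 6.5. For escalation halted after Week 24: "Dosing in these subjects will be discontinued when dose-escalation is stopped". For build-up failure before then: "Dosing will be stopped after the Week 24 Visit; and the subject will be asked to return to the Clinical Research Center 14 days" after the last dose. In both cases, "An Early Discontinuation visit is to occur 14 days from the last dose of study product". That visit repeats the Exit procedures, including the VAS and SPT, without the food challenge. Appendix 1 marks the VAS at Baseline and Visit 03 only.

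**The concern.** A site cannot follow both 6.13 and 6.5 for a subject who is still up-dosing at Week 34 and has not qualified for the challenge. Under 6.13 the assignment is released at Week 34, and the final visit comes afterwards.

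The VAS is the outcome most exposed. Protocol 6.7 makes it a single integrated judgement by the investigator. With one post-baseline value per subject, that value determines the whole change score, and there is no blinded reading to fall back on. SAP 10.12 reports the between-arm difference in mean change with a 95% confidence interval in the Safety population, which includes escalation failures. Under SAP 7.8 the site requests scheduled unblinding, so following 6.13 puts the assignment at the rater's site before the rating. The SPT is a measured diameter and is less open to expectation. The SAP does not flag either result when it is obtained after unblinding.

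**Working it through.** The plan gives no figure to reproduce. The check is timeline arithmetic.

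**Inputs**
- Early Discontinuation visit: last dose + 14 days, i.e. L + 2 weeks (Protocol 6.5).
- Last dose L: about Week 0 for a Visit 01 failure; Week 24 for a build-up halt before Week 24; the halt week W for a halt after Week 24, up to Week 34 (Protocol 3.2).
- Unblinding week U: 34 under the dated sentence of 6.13. If the first sentence of 6.13 is read as an instruction and the floor of 3.3 and 4.3.1 is applied, U is the later of the failure week and Week 24.

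**Formula**

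Gap = (L + 2) − U. A positive gap means that the VAS and SPT follow unblinding.

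| Subject | L | Visit | Gap, Week 34 sentence | Gap, general wording with Week 24 floor |
|---|---|---|---|---|
| Visit 01 failure | 0 | 2 | 2 − 34 = −32 | 2 − 24 = −22 |
| Build-up halt before Week 24 | 24 | 26 | 26 − 34 = −8 | 26 − 24 = 2 at most |
| Halt at Week 26 | 26 | 28 | 28 − 34 = −6 | 28 − 26 = 2 |
| Halt at Week 30 | 30 | 32 | 32 − 34 = −2 | 32 − 30 = 2 |
| Halt at Week 32 | 32 | 34 | 34 − 34 = 0 | 34 − 32 = 2 |
| Still dosing at Week 34 | 34 | 36 | 36 − 34 = 2 | 36 − 34 = 2 |

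Under the Week 34 sentence the gap is L − 32. It is positive only when the last dose is after Week 32, and it reaches 2 weeks at L = 34. Under 6.5 and SAP 7.8 no subject is unblinded before the rating.

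**Visit windows.** Protocol 6.12 lets visits for scheduled blood draws fall within 2 weeks of schedule, and this visit includes the IgE and IgG4 draw. If that window applies, the 2-week gap at L = 34 could be anything from 2 − 2 = 0 to 2 + 2 = 4 weeks.

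**How many subjects.** The documents do not say. Protocol 9.3 plans for 3 or 5 subjects per arm without an exit challenge, but that count also covers Visit 01 failures, dropouts and earlier halts. Under SAP 3.2.2 uninterrupted up-dosing reaches 300 mg/day at about Week 18 or 20, so a subject short of it at Week 34 is 34 − 20 = 14 to 34 − 18 = 16 weeks behind. Few subjects are likely to be in that position.

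**Weight of one subject.** With 50/2 = 25 per arm, one subject supplies 1/25 = 4% of an arm's VAS change scores, if all contribute. A shift of d mm in one rating moves the arm mean by d/25 mm. This is a weight, not an estimate of bias.

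**The case against.** The strongest reply is that 6.5 already states the right order for every subject and SAP 7.8 repeats it, so 6.13 is loose wording that a site would read in their light. SAP 7.8 also releases the assignment only to the person who requests it, who need not be the VAS rater. In addition, the rater already weighs the reaction history (Protocol 6.7), and SAP 7.7 accepts that dosing symptoms hint at assignment. All of this limits the harm. It does not remove the contradiction: 6.13 is the section on blinding, its Week 34 sentence carries a date, and a hint is not disclosure. Protocol 6.13.2 does not settle the matter either. It restricts unblinding before the exit challenge, which escalation failures never have.

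Four stronger readings are tempting, and the documents do not support them.

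- **Every escalation failure is rated unblinded.** The Week 34 sentence does not do this for halts up to about Week 32, because the visit then falls at or before Week 34. For those subjects, after Visit 01, the conflict rests only on the general wording about escalation failure, which sets no date.
- **The gap is much longer for early build-up failures.** Read alone, the first sentence of 6.13 would give 26 − 6 = 20 weeks for a failure at Week 6. The Week 24 floor rules this out and holds the gap to 2 weeks at most. For Visit 01 failures the same floor falls about 22 weeks after the visit.
- **The synopsis and 3.3 contradict 6.5 as well.** Their shorter wording can be read consistently with 6.5, which lists the VAS and SPT, adds the challenge, and unblinds after all of them.
- **A subject who reaches 300 mg/day just before Week 34 is unblinded before the challenge.** Protocol 4.3.1 protects subjects eligible for an exit challenge until it takes place, and 6.8.4 allows the Exit visit up to Week 36.

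**Conclusion.** The contradiction is real, and its scope is narrow. For subjects whose last dose is after about Week 32, Protocol 6.13 directs unblinding up to about 2 weeks (nominal) before the only post-baseline VAS and the exit SPT, against 6.5 and SAP 7.8. For earlier halts after Visit 01 it is an ambiguity, worth at most 2 weeks once the Week 24 floor is applied. Visit 01 failures are not affected.

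A reader might infer that the efficacy conclusion is at risk. It is not. Under SAP 7.3 an escalation failure is a non-responder with the screening tolerated dose carried forward (the documented exception for free peanut consumption does not depend on this visit), so nothing recorded at the late visit enters the primary or key secondary analyses. The VAS and SPT are secondary and outside the testing hierarchy of SAP 9.3.

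The conclusion assumes that sites follow 6.13 as written, that the visit falls on its nominal day, and that the released assignment reaches the rater. The number of subjects is unknown but probably small, and no size of bias can be derived from the documents. The point is worth correcting because the error is avoidable and the remedy is cheap.

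**What to change.** In Protocol 6.13, replace the first three sentences with one rule:

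> *Scheduled unblinding occurs only after all Exit or Early Discontinuation procedures (DBPCFC if eligible, VAS, SPT) are complete or, if that visit is not attended, after study exit; for escalation failures, not before Week 24. Emergency unblinding is unchanged.*

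This adopts the order already in 6.5 and SAP 7.8 and keeps the floor of 3.3 and 4.3.1. A cross-reference from the synopsis, 3.3 and 4.3.1 would be helpful but is optional. Protocol 6.5 and SAP 7.8 need no change for this purpose.

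If any subject has already been unblinded under 6.13, use the unblinding date held in TEMPO to report, by arm, how many VAS results were obtained after unblinding. Treat this as a count of possible exposure, since the date records a release to one requester and not what the rater knew.

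The cost is a wording change in one section and, if needed, one count. Some escalation failures would learn their assignment about two weeks later, which may delay ARC002 entry for those on placebo.

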6.13.1 Securing Blinding and Randomization Information

ARC or contractor will manufacture, package, label, store, and distribute the study product. During site visits, the site monitor checks the pharmacist or clinic logs to ensure that appropriate randomization assignments are received, recorded, and maintained.

6.13.2 Requirements for an Unblinding

Prior to the exit DBPCFC assessment, a subject can be unblinded only when needed for making medical decisions regarding the care of a subject. The decision of unblinding will be made in collaboration with the sponsor's Medical Monitor.

If a life-threatening event occurs, the subject should be treated as if the subject received active study product. For all unscheduled events that require unblinding, the investigator will contact the clinical monitor who will coordinate with the sponsor's representatives.

6.13.3 Breaking the Blind

In case emergency unblinding is necessary, TEMPO[™] allows study personnel with appropriate permissions to request unblinding for a specific subject. An email is then sent to appropriate sponsor and CPWW safety designees informing them of the blinding. A built-in audit trail documents the unblinding process and the persons involved.

6.13.4 Documenting an Unblinding

Any premature unblinding requires a full written account by the site study physician of the event(s) that necessitated unblinding of the study medication for an individual participant. This account includes the reason(s) for unblinding, the name of the sponsor's medical monitor who was notified of the unblinding, the names of the unblinded individual staff members and the date and time the unblinding occurred.

7. Safety Monitoring

This section defines the types of adverse events that should be reported and outlines the procedures for appropriately collecting, grading, recording and reporting them.

7.1 Definitions for Recording of Safety Events

All safety events observed under this protocol are reported through the data system for the duration of the study. Some safety events arising under certain defined conditions are recorded on specific forms as follows.

- Safety events related to accidental food exposure are recorded on a Food Allergy Episode form and are not reported on an adverse event form unless the event is considered a serious adverse event, as defined below (Section 7.2).
- Any allergic symptoms due to dosing will be recorded directly on the Escalation Dosing form (also referred to as a Study Product Administration form).
- For any event occurring after a subject has signed the informed consent form that meets the definition of anaphylaxis, an Anaphylaxis Episode form will be completed and forwarded to the Coordinating Center within 24 h of its occurrence and/or the sites being notified of the event (see also Section 7.7.2), if the event is associated with any of the following:
 - An emergency room visit;
 - Hospitalization;
 - More than 2 doses of epinephrine being given as treatment for the same episode;
 - Assessment of the anaphylaxis as severe, as defined in Appendix 3.
- If any safety event meets the definition of a serious adverse event (whether or not related to dosing), it will also be recorded on an adverse event (AE)/serious adverse event (SAE) form. Skin prick test and food challenge reactions that occur in the clinic are captured on study specific forms and are not reported on an adverse event form unless the event is considered a serious adverse event, as defined below. All serious adverse events are reported on the AE/SAE form set in addition to the Skin Prick form or an Oral Food Challenge form if the event occurred during one of these procedures. All other safety events that occur throughout the study are reported on the AE/SAE form set.

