1.2 Peanut OIT

Varshney et al¹⁵ conducted a double-blind placebo controlled study of an OIT protocol in subjects with severe allergy to peanut protein and consistently demonstrated an increase in the dose of allergen tolerated by the subjects versus baseline with a good safety profile.

In addition, peanut OIT has been administered under IND (Investigational New Drug Application) at Duke and Arkansas and under a separate IND at Stanford.^{*} A total of 44 cases from Duke/Arkansas were analyzed and 14 cases from Stanford. Efficacy was demonstrated in 26 cases (17 active and 9 placebo) matching the published information. Sixteen out of 17 active subjects were escalated to a dose between 2400 and 4000 mg over a year. Oral food challenge results were significantly better for the active treatment group than the placebo group where both groups tolerated a mean of 12 mg of peanut protein at baseline, while at one year the mean for the active treatment group was 5000mg of protein and for the placebo group 280 mg of peanut protein (P < 0.001 by Wilcoxon rank-sum test).¹⁵

Dosing symptoms were typical for OIT protocols including rash, wheezing, rhinorrhea, sneezing, itching, abdominal pain, nausea, vomiting, and diarrhea. Symptoms were noted in both the active treatment and the placebo group. Of the 39 cases on active treatment, 4 doses of epinephrine were administered – 2 during dosing and 2 during double-blind, placebo controlled food challenges (DBPCFCs). The Stanford data reported on 14 subjects who were dosed with peanut OIT and dosing symptoms severity and rate were similar to those reported in the Duke/Arkansas data.

These published findings, along with the additional clinical data, are the basis for a Phase II trial to investigate peanut OIT for efficacy and safety in desensitizing peanut allergic subjects. Protocol ARC001 is designed to be a double-blinded, placebocontrolled study establishing the efficacy of CPNA for conducting oral immunotherapy. Protocol ARC002 and any additional follow-on studies will be related but separate openlabel protocols designed to demonstrate the safety of daily dosing with CPNA for an extended period (months to years), to confirm unblinded the efficacy of OIT with CPNA at a dose of 300 mg/d of peanut protein in the former ARC001 placebo population, to provide an option to explore unblinded the safety and tolerability of OIT, and to maintain any desensitization that may have been achieved by subjects.

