#### 2.3.3 Exploratory endpoints

Exploratory safety endpoints include:

- Epinephrine use
- Occurrence of anaphylactic reaction episodes

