## **11.3 Anaphylaxis Episodes**

All reported anaphylactic reaction episodes will be listed by subject. The number of subjects experiencing such a reaction, the number of reactions per subject, and the total number of reactions reported will be summarized. Episodes will also be summarized by the episode trigger.

These summaries will be repeated for:

- Episodes where epinephrine is administered on the same date (based on the Concomitant Medication CRF pages)
- Episodes where epinephrine is not administered on the same date
- Episodes which occur on the same date as accidental exposure to a food allergen
- Episodes which do not occur on the same date as accidental exposure to a food allergen

These summaries will be produced separately for the Safety and Screening DBPCFC Only populations.

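### Read literally, Protocol 7.1 requires an Anaphylaxis Episode form only when one of four 24-hour reporting triggers is met, so the SAP's anaphylaxis tables may miss mild or moderate episodes that meet none

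*Protocol*

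**What the plan says.** Protocol 7.1 assigns each kind of safety event to a form. For any event after consent "that meets the definition of anaphylaxis, an Anaphylaxis Episode form will be completed and forwarded to the Coordinating Center within 24 h", subject to a condition: "see also Section 7.7.2), if the event is associated with any of the following". Four triggers follow:

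- an emergency room visit;
- a hospital admission;
- "More than 2 doses of epinephrine being given as treatment for the same episode";
- a grade of severe under Appendix 3.

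Protocol 7.7.2 repeats the same four triggers and says that the DMC asked for these episodes to be reported within 24 hours.

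SAP 2.3.3 lists as an exploratory safety endpoint "Occurrence of anaphylactic reaction episodes". Under SAP 11.3, "All reported anaphylactic reaction episodes will be listed by subject". Subjects with an episode, episodes per subject and total episodes are then summarized, with subsets that include "Episodes where epinephrine is not administered on the same date". The results go to Table 14.3.3.1 (Safety population), Table 14.3.3.2 (Screening DBPCFC Only population) and Listing 16.2.10. None of these SAP places mentions the four triggers.

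**The concern.** A rule that fits expedited reporting appears to have been written as the rule for whether the form is filled in at all. If sites follow 7.1 as written, an event can meet the Appendix 3 diagnostic criteria, be staged mild or moderate, be treated in the research center, and produce no Anaphylaxis Episode form. If the SAP tables are built from that form, the event is not counted, and nothing in the table titles tells the reader so.

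Anaphylaxis is among the principal risks named in Protocol 1.6.1. A table that appears to count anaphylactic episodes, but counts only those that met a reporting trigger, would be read as a fuller account than it is.

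**Working it through.** No rate, power or alpha is stated for anaphylaxis, so there is no plan figure to reproduce. The check is a comparison of the passages, followed by what little can be bounded.

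**1. What the condition governs.** The sentence in 7.1 has two verbs ("an Anaphylaxis Episode form will be completed and forwarded to the Coordinating Center within 24 h") and a single condition after them. The section heading concerns recording, not expedited reporting. No other section tells sites to complete the form for anaphylaxis that meets no trigger.

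**2. Which episodes can fall outside.** Appendix 3 has three stages. Stage 3 (severe) is itself a trigger. Stages 1 and 2 need an ER visit, an admission or more than two epinephrine doses. Stage 2 includes stridor and shortness of breath with retractions, so it is not trivial. Under Protocol 6.8.3, a reaction that needs two or more epinephrine doses halts that subject's escalation, whereas the form's dose trigger needs more than two. A stage 2 reaction treated in clinic with exactly two doses, without ER visit or admission, would therefore halt escalation but not require the form.

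**3. Where such an episode is recorded instead.**

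| Setting | Form under Protocol 7.1 | Also on the AE form? |
|---|---|---|
| Study-product dosing | Escalation Dosing form, as symptoms | Not expressly excluded |
| Clinic food challenge | Oral Food Challenge form | Only if serious |
| Accidental food exposure | Food Allergy Episode form | Only if serious |
| Other | AE/SAE form set | Yes |

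The event is therefore not lost to the database. It is simply not labelled as anaphylaxis.

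**4. Whether the SAP restores the label.** SAP 11.3 names no source form. SAP 7.7 lists anaphylaxis episodes separately from adverse events, and Listing 16.2.10 is separate from the AE listings, which points to the dedicated form as the source. There is no rule applying the Appendix 3 criteria to the dosing, challenge, food-allergy or AE records. The SAP addendum, section 2.1, codes allergic AEs to the preferred term hypersensitivity with a symptom-level sub-classification, which does not identify anaphylaxis either.

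**5. Size.** Let q be the probability that a mild or moderate episode meets at least one trigger. If the form is the only source, the share of such episodes missed is 1 − q. The documents give no q. Over an assumed range:

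- q = 0.10: 90% missed
- q = 0.25: 75% missed
- q = 0.50: 50% missed
- q = 0.75: 25% missed

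The only related data are in Protocol 1.2: "Of the 39 cases on active treatment, 4 doses of epinephrine were administered", two during dosing and two during challenges. No single dosing or challenge event there can have had more than two doses, so 0 of 39 cases met the dose trigger in those settings. The exact upper limit is 1 − 0.05^(1/39) = 7.4% (one-sided 95%), or 1 − 0.025^(1/39) = 9.0% (two-sided 95%). This bounds one trigger only. The cases came from academic INDs, 16 of the 17 active subjects in the efficacy subset reached 2400 to 4000 mg rather than the 300 mg target here, and the text does not say whether the treated events were anaphylaxis. ER and admission rates are not given, so q remains unknown.

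**6. Effect on the comparison between arms.** If each episode is captured with the same probability c in both arms, and the expected episode rates are a on CPNA and b on placebo, the table shows ca and cb. The difference shrinks to c(a − b), while the ratio ca/cb = a/b is unchanged.

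**The case against.** The strongest reply is that the triggers were meant only for the 24-hour clock. Section 7.7.2 presents them that way, and the clinic-epinephrine rules in 6.8.3 cite 7.1 and 7.7.2 together as a 24-hour reporting requirement. SAP 11.3 plans for episodes without epinephrine, which suggests that its authors expected a wider set than trigger-meeting events. This may well be the intent. It does not settle the matter, because 7.1 is the instruction sites follow and does not separate completing from forwarding. An episode without epinephrine could also enter through an ER visit, so that SAP subset does not prove a wider capture.

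A second reply is that the information appears elsewhere. Graded symptoms are summarized for every challenge and escalation dose (SAP 10.5 and 10.6), epinephrine use is tabulated by time point and frequency (SAP 11.1), and medications given for anaphylactic reactions are listed (SAP 10.2). This stands, and it limits the harm. It does not supply a count of anaphylactic episodes.

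Third, the SAP promises only reported episodes, and the endpoint is exploratory. Both points stand. The primary and key secondary tests are untouched.

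**Conclusion.** The mismatch is real: the literal recording rule in Protocol 7.1 is narrower than the endpoint the SAP reports, and no section closes the gap. Mild or moderate anaphylaxis that meets no trigger may be missing from Tables 14.3.3.1 and 14.3.3.2. This rests on two assumptions: that sites apply 7.1 as worded, and that the tables are built from the Anaphylaxis Episode form. The second is likely but not stated. The size cannot be estimated from the documents.

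A reader might infer more, and the documents do not support it:

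- *Most mild and moderate anaphylaxis is lost.* That needs q below 0.5, and no q is given.
- *The triggers are a severity filter.* Only one is a severity grade; two are care settings and one is a dose count. A mild episode with an ER visit is captured.
- *Dosing reactions never reach the AE form.* Section 7.1 does not exclude them, Section 7.6 lists home symptom logs as a source of AEs, and SAP 10.3 has AE onset periods for Visit 01 and up-dosing visits.
- *The split by epinephrine use is empty by construction.* Episodes entering through an ER visit, an admission or a severe grade can fall on either side.
- *Home reactions are counted and clinic reactions are not, or CPNA is made to look safer.* No capture rate by place or arm is given, and equal capture preserves the ratio between arms.

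This should be corrected as a matter of safety reporting. It has no bearing on power or type I error.

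**What to change.** - **Protocol 7.1:** require an Anaphylaxis Episode form for every event after consent that meets the Appendix 3 diagnostic criteria, whatever its stage, setting or treatment. Keep the four triggers only as the test for forwarding within 24 hours, in line with 7.7.2.
- **SAP 11.3:** name the source form, state that all events meeting Appendix 3 are counted, and add a summary by Appendix 3 stage.
- **Data already collected:** query sites about dosing, challenge and food-allergy reactions that meet Appendix 3 but have no form. Under SAP 11.1, sites are already queried about actual epinephrine use and the event treated, so this extends an existing process.
- **If capture cannot be widened:** footnote Tables 14.3.3.1 and 14.3.3.2 as covering only episodes that met a trigger.

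The cost is a reworded sentence in 7.1, short additions to SAP 11.3, an existing form completed for some more events, and one query round. No new study procedure is needed.
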